Estimates of the endpoints at V14, V28, V42 (corresponding to the end of the 1st, 2nd and 3rd month of training) and their 95% confidence intervals will be presented as per the comparisons listed in Table 5 except for IQOS-2 and Dual-2 groups as they did not participate in any exercise training. Estimates of study arms and pairwise comparisons of study arms will be tabulated over all visits as well as separately for each visit.

An example of SAS code for the model to be used is provided below:

```
proc mixed data= _DATA_ method=reml order=data;
class SUBJECT VISIT ARM SEX CC_CONS_GRP;
model ENDPOINT = ARM SEX AGE CC_CONS_GRP DAILY_CC_USE VISIT VISIT*ARM
/ddfm = kr;
random SUBJECT / subject = SUBJECT;
repeated VISIT / type=ar(1) subject = SUBJECT;
lsmeans ARM / diff=control("CC") CL alpha=0.05 bylevel e;
lsmeans ARM / diff=control("IQOS-1") CL alpha=0.05 bylevel e;
lsmeans VISIT*ARM / diff=control("VISIT#X" "CC") CL alpha=0.05 bylevel e;
```

Confidentiality Statement

Philip Morris Products SA.	Statistical Analysis Plan	Confidential
P1-EXC-01-EU	Final 2.0	Page 43 of 71
Related to PMI-RRP-WKI-112487		SAP P1-EXC-01-EU

```
lsmeans VISIT*ARM / diff=control("VISIT#X" "IQOS-1") CL alpha=0.05 bylevel
e;
run;
```

Estimates of variability (e.g. "Covariance Parameter Estimates") from the statistical model will be reported (at least in the original statistical output listings) and may be used to power future similar studies.

The average work rate during each interval at each training session, average heart rate during each training session, time spent at various percentages of maximal work rate and time spent at various percentages of maximal heart rate will be summarized using only descriptive statistics. For the time spent at maximal work rate or heart rate the data will be summarized at V5, V14, V29 and V41 as subjects will be on training program 1 at these visits.

9.6.1.1.4 To evaluate changes in physiological parameters and perception of exertion and capacity in subjects switching to IQOS, continuing to smoke cigarettes and being smoking abstinent

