where W_{ij} is the work rate for subject *i* at time *j* α and β are the minimum and maximum lactate levels respectively. The parameter η_i represents the workrate that elicits a response midway between α and β_i , and δ is a shape parameter. Lastly, the error term is modelled as ε_{ij} . Note that β_i and η_i are modelled as random effects to allow for variations in the lactate curve between subjects. An example of the sas code is as shown below, starting parameters may be found using proc nlin without the random effects. The number of random effects may be adjusted depending on model fit.

```
proc nlmixed data= data ;
  parms b0=xx e0=xx a=xx d=xx s2=xx s2b1=xx s2b2=xx cb12=xx;
  beta = b0 + bi;
  eta = e0 + ei;
  pred = beta+(a-(beta))/(1+exp(d(ln(w)-ln(eta))));
  model vo2 ~ normal(pred,s2);
   random bi ei ~ normal([0,0],[s2b1,cb12,s2b2]) subject=subject;
run;
```

Using the fitted models, we will back-calculate the value of W^* (conditional on β_i and η_i) that elicits a response of y=4 mmol (Heck 1985) using the following formula for each arm and visit.

$$W^* = \hat{\eta} \left(\frac{\hat{\alpha} - 4}{4 - \hat{\beta}} \right)^{\frac{1}{\hat{\delta}}}$$

Note that $\hat{\alpha}$, $\hat{\beta}$, $\hat{\delta}$ and $\hat{\eta}$ are the respective estimates from the fitted model. Within each arm, we will present the change in workload at a lactate level of 4mmol from V3 to V43. The mean curve estimated from the model for Cigarette, IQOS-1, IQOS-2 and SA will be plotted versus workload for each arm and visit, in these plots a horizontal line at 4 mmol will be drawn as well. The same plot will be done for Cigarette, IQOS-1, IQOS-2, Dual-1 and Dual-2.

For the endpoints VO₂ and heart rate (V4 and V43), a linear mixed effects model will be used with the restricted maximum likelihood method for estimation of the parameter in the various (cigarette, IQOS-1 and SA) arms versus workload. Each endpoint will be fitted with workload, age, visit, sex, arm, visit*arm, baseline cigarette consumption at V1 and daily cigarette

Data and information contained in this document are considered to constitute trade secrets and confidential commercial information, and the legal protections provided to such trade secrets and confidential information are hereby claimed under the provisions of applicable law. No part of this document may be publicly disclosed without the written consent of Philip Morris Products S.A

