Philip Morris Products SA.	Statistical Analysis Plan	Confidential
P1-EXC-01-EU	Final 2.0	Page 45 of 71
Related to PMI-RRP-WKI-112487		CAD DI EVC AL EU

consumption as covariates. Additional covariates may be added as appropriate based on the results of the step wise modelling in section 9.6.1.1.1.

The mean curve estimated from the model for the CIGARETTE, IQOS-1, IQOS-2 and SA arm will be plotted versus workload for each arm and visit. The curves will be plotted for CIGARETTE, IQOS-1, IQOS-2, Dual-1 and Dual-2 in one plot as well.

An example of SAS code for the model to be used is provided below:

```
proc mixed data= _DATA_ method=reml order=data;
class SUBJECT VISIT ARM SEX CC_CONS_GRP;
model ENDPOINT = WORKLOAD ARM SEX AGE CC_CONS_GRP DAILY_CC_USE VISIT
VISIT*ARM /ddfm = kr;
random SUBJECT / subject = SUBJECT;
run;
```

Estimates of variability (e.g. "Covariance Parameter Estimates") from the statistical model will be reported (at least in the original statistical output listings) and may be used to power future similar studies.

9.6.1.1.5 To monitor trends of daily physical activity levels during the study in subjects switching to IQOS, continuing to smoke cigarettes and being smoking abstinent

The SAS procedure PROC MIXED will be used with the restricted maximum likelihood method for evaluation of the aggregated data for step counts from the mobile health (mHealth) wearable in the study arms over time. For step count, the dependent variable will be the average step count by month, this is derived by averaging the daily step count from V4 to V14 (Month 1), V14 to V28 (Month 2) and V28 to V43 (Month 3) divided by the number of valid days during each defined period. For a definition of valid day for step count refer to section 9.1.6.

The variables Arm, Visit, Visit*Arm, Sex, age, and baseline cigarette consumption at V1, baseline step count (see section 9.1.3) will be considered as covariates, subject will be used as a random effect. The Kenward-Roger adjustment for degrees of freedom will be use.

Estimates of the monthly step count and their 95% confidence intervals within each arm will be reported and also between arms as per Table 5.

An example of SAS code for the model to be used is provided below:

```
proc mixed data= _DATA_ method=reml order=data;
class SUBJECT MONTH ARM SEX CC_CONS_GRP;
model ENDPOINT = ARM SEX AGE CC_CONS_GRP MONTH MONTH*ARM /ddfm = kr;
random SUBJECT / subject = SUBJECT;
lsmeans ARM / diff=control("CC") CL alpha=0.05;

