Table 15.2.2.4.4.1: Regression Coefficients for Analysis of Heart Rate – AEECS	
Table 15.2.2.4.5.1: Regression Coefficients for Analysis of Oxygen Uptake –	
AEECS	

Confidentiality Statement

Philip Morris Products SA.	Statistical Analysis Plan	Confidential
P1-EXC-01-EU	Pending Approval 0.1, CURRENT, IN PROGRESS	Page 68 of 71
Related to PMI-RRP-WKI-112487		DD SME01 810208 SAD D1

Table 15.2.2.4.6.1: Descriptive Statistics of Physiological and Respiratory	
Parameters by Workload - AEECS	
Table 15.2.2.4.7.1: Descriptive Statistics of RPC (continuous) by Sex – AEECS	
Table 15.2.2.5.1.: Analysis of the Average Step Count by Month – AEECS	X
Table 15.2.2.5.2.: Regression Coefficients for Analysis of Average Step Count	
by Month – AEECS	
Table 15.2.2.5.3: Descriptive Statistics of mHealth variables - AEECS	Х
Table 15.2.2.6.1: Analysis of the Changes in Biological Health Markers fromBaseline at V14, V28 and V43 – AEECS	
Table 15.2.2.6.2: Regression Coefficients for Analysis of Changes in Biological	
Health Markers from Baseline – AEECS	
Table 15.2.2.6.3: Descriptive Statistics of Biological Health Markers - AEECS	
Table 15.2.2.6.4: Analysis of the Changes in Biological Health Markers from	
Baseline at V14, V28 and V43 – AEBECS	
Table 15.2.2.6.5: Regression Coefficients for Analysis of Changes in Biological	
Health Markers from Baseline – AEBECS	
Table 15.2.2.6.6: Descriptive Statistics of Biological Health Markers - AEBECS	
Table 15.2.2.7.1: Analysis of the Changes in Body Fat and Waist Circumference	
from Baseline (Acute Effect, V4) – AEECS	
Table 15.2.2.7.2: Analysis of the Changes in Body Fat and Waist Circumference	
from Baseline (Exercise Effect, V43) – AEECS	
Table 15.2.2.7.3: Regression Coefficients for Analysis of the Changes in Body	
Fat and Waist Circumference from Baseline– AEECS	
Table 15.2.2.7.4: Summary of Body Fat and Waist Circumference by ProductUse Category - AEECS	
Table 15.2.2.7.5: Analysis of the Changes in Body Weight from Baseline byMonth – AEECS	
Table 15.2.2.7.6: Regression Coefficients for Analysis of the Changes in Body	
Weight from Baseline– AEECS	
Table 15.2.2.7.7: Summary of Body Weight by Product Use Category – AEECS	
Table 15.2.2.8.1: Descriptive Statistics for Exhaled CO – AEECS	
Table 15.2.2.8.2: Descriptive Statistics for Biomarkers of Exposure - AEECS	Х
Table 15.2.2.8.3: Descriptive Statistics for Exhaled CO – AEBECS	
Table 15.2.2.8.4: Descriptive Statistics for Biomarkers of Exposure - AEBECS	

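### The heart-rate and VO2 versus workload model forces parallel straight lines, leaves out V3, and can understate the SEs of its visit and visit*arm coefficients

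*SAP*

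**What the plan says.** In SAP 9.6.1.1.4 the sentence introducing the model reads "For the endpoints VO₂ and heart rate (V4 and V43), a linear mixed effects model will be used", estimated by restricted maximum likelihood. The prose lists the terms: "Each endpoint will be fitted with workload, age, visit, sex, arm, visit*arm, baseline cigarette consumption at V1 and daily cigarette" consumption. The sample code agrees. It has "model ENDPOINT = WORKLOAD ARM SEX AGE CC_CONS_GRP DAILY_CC_USE VISIT", continued on the next line by VISIT*ARM with Kenward-Roger degrees of freedom. The class statement is "class SUBJECT VISIT ARM SEX CC_CONS_GRP", so workload is continuous. The only covariance statement is "random SUBJECT / subject = SUBJECT".

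From this fit the SAP plans mean curves against workload for each arm and visit (Figures 15.1.4.3 to 15.1.4.6). It also plans coefficient tables such as "Table 15.2.2.4.4.1: Regression Coefficients for Analysis of Heart Rate – AEECS", with a counterpart for oxygen uptake, and covariance parameter estimates that may help to size later studies. No arm contrast or confidence interval is specified for this model.

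Objective 4 in SAP 3.1 and Protocol 3.1 defines heart rate and oxygen uptake during the VO2max test at V3, V4 and V43.

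**The concern.** The readings run from rest to volitional fatigue in 25 W steps (Protocol 7.6.1). A figure headed as a heart-rate or oxygen-uptake curve by arm invites the reader to compare shapes, and this model has already made the slopes equal. A switching or training effect that grows or shrinks with load would be averaged into a constant shift.

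Without V3, both modelled visits fall after randomization. The model therefore gives no acute change from baseline, and its V4-to-V43 contrast starts after the switch.

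Several readings come from each test. If a subject's whole trace is a little high or low on a given day, those readings carry less information about change between visits than the model assumes. The visit*arm coefficients, which compare change between arms, would then look too precise, and the variance estimates offered for future planning would mislead.

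**Working it through.** The documents give no SE, variance or sample size for this model, so there is no plan figure to reproduce.

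**Parallel lines (no assumption needed).** The fitted mean for arm a and visit v at workload W is: intercept + arm(a) + visit(v) + visit*arm(a,v) + covariate terms + b·W. The slope is b in every arm-by-visit cell. The gap between any two lines does not contain W, so it is the same at rest as at 200 W.

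The clause allowing further covariates does not change this. It points to the stepwise results of 9.6.1.1.1, whose candidate list has no workload interaction and no covariance term. By contrast, the lactate model in 9.6.1.1.4 is fitted separately by arm and visit, so its shape may differ.

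**SE of a change between visits.** Inputs:
- T = 2 visits (SAP 9.6.1.1.4).
- K = 8 readings per test, assumed: rest plus seven 25 W steps, a peak of 175 W. The 200 W example in Protocol 7.6.2 would give 9.
- Residual variance s_e² = 4² = 16, assumed.
- Test-day (subject-by-visit) variance s_sv² = 3² = 9 or 5² = 25, assumed.

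Per subject, with balanced data:
- True variance of the V4-to-V43 change = 2·s_sv² + 2·s_e²/K.
- Residual variance the model will fit = s_e² + K(T−1)·s_sv²/(KT−1).
- Model variance of the change = 2 × fitted residual / K.

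| Test-day SD | True variance | Fitted residual | Model variance | SE ratio |
|---|---|---|---|---|
| 3 bpm | 18 + 4 = 22 | 16 + 72/15 = 20.8 | 5.2 | √(5.2/22) = 0.49 |
| 5 bpm | 50 + 4 = 54 | 16 + 200/15 = 29.3 | 7.33 | √(7.33/54) = 0.37 |
| 0 | 4 | 16 | 4 | 1.00 |

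The number of subjects cancels, so the same ratios apply to visit*arm. A nominal 95% interval built on these SEs would cover about 66% and 53% in the first two rows.

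Sensitivity with K = 9 and test-day variance as a multiple of residual variance:

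| Multiple | 0 | 0.1 | 0.25 | 0.5 | 1 | 2 |
|---|---|---|---|---|---|---|
| SE ratio, visit change | 1.00 | 0.74 | 0.59 | 0.48 | 0.39 | 0.33 |

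**SE of a between-arm difference at one visit.** True variance per subject is s_s² + s_sv² + s_e²/K, where s_s² is the between-subject variance. The model uses fitted subject variance + fitted residual/K. The fitted subject variance is s_s² + s_sv²/T + (s_e² − fitted residual)/(KT).
- Between-subject SD 5, test-day SD 5: true 25 + 25 + 2 = 52. Model 25 + 12.5 − 0.83 + 3.67 = 40.3. Ratio 0.88.
- Between-subject SD 10, test-day SD 3: true 100 + 9 + 2 = 111. Model 100 + 4.5 − 0.3 + 2.6 = 106.8. Ratio 0.98.

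**Where the test-day variance goes.** For test-day variance 9, the residual absorbs 4.8 and the subject component 4.2. For 25, they absorb 13.3 and 11.7.

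**Simulation check.** REML fits with 3 arms of 20, K = 9, residual variance 1, between-subject variance 2, 150 runs per setting, no slope variation:

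| Coefficient | Test-day variance 0.25: ratio (coverage) | Test-day variance 1: ratio (coverage) |
|---|---|---|
| visit*arm | 0.56 (69%) | 0.36 (48%) |
| Arm difference at V4 | 1.01 (97%) | 0.86 (89%) |
| Workload slope | 1.16 (97%) | 1.30 (100%) |

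With a subject slope SD of 0.005 per W and test-day variance 0.5, the workload-slope ratio fell to 0.73 (coverage 85%).

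**The case against.** The strongest reply is that unconstrained results are already planned. SAP 9.6.1.2.4 summarizes heart rate and VO2 within each arm, for each visit, at rest and at each 25 W step, and Table 15.2.2.4.6.1 reports statistics by workload. A reader will see V3, and will see whether arms diverge with load, though without adjustment. This stands and limits the harm.

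Three stronger readings are tempting and are not supported:
- That the model ignores clustering. The subject intercept absorbs whatever a subject's readings share across visits. Only subject-by-visit and slope variation are missing.
- That its SEs are far too small throughout. This applies to visit and visit*arm coefficients only. Between-arm SEs at a visit are mildly low, and the workload-slope SE can err either way.
- That the figures cannot show any effect of switching or training. The visit-by-arm term lets each line shift, so a lower heart rate at the same load can be seen. No section names the slope as the target of the endpoint.

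It is also fair that the study is descriptive, that no interval is specified for this model, and that table shells are a separate document, so whether SEs will be printed is unknown. Against that, Protocol 12.5 promises arm differences with 95% confidence intervals for this objective.

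**Conclusion.** The common slope and the absence of V3 from the model are certain from the text and code. The planned curves will be parallel straight lines whatever the data show.

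The understated SEs for visit and visit*arm are conditional: none if test-day variance is zero, and a ratio of 0.49 to 0.37 under the illustrative heart-rate values. Those variances and the number of readings are assumptions that the documents neither support nor contradict, and no VO2 figures were assumed. Kenward-Roger degrees of freedom do not help, because they work within the stated covariance structure. The reported variance components will also mix test-day variance into the subject and residual terms.

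The reach is limited to the model-based figures, coefficient tables and variance estimates for these two endpoints.

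**What to change.** - Add a random subject-by-visit intercept, and a random workload slope if it converges. The slope matters more once workload interactions are in the model. The training-intensity model in 9.6.1.1.3 already adds within-subject structure through "repeated VISIT / type=ar(1) subject = SUBJECT", so an extra covariance term is no departure in style.
- Add WORKLOAD*ARM*VISIT with its lower-order terms for the product-use groups large enough to support it. The lines remain straight but need no longer be parallel.
- Include V3, either as a baseline covariate or as a third visit.

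The cost is a few lines of code and more parameters. With all six product-use groups of SAP 9.1.1, two visits need 6 × 2 = 12 slopes instead of 1 (11 extra), and three visits need 6 × 3 = 18 (17 extra). Slopes in small Dual groups may be poorly estimated, so those groups could keep a common slope, with that stated in the figure. If test-day variance proves negligible, the added random intercept changes little.

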9.1.3 Definitions for Statistical Data Analysis

The baseline value for any given parameter will be the last assessment prior to randomization for the subjects randomized to either IQOS, cigarette or SA arms.

Change from baseline (i.e. difference of post baseline value compared to baseline value) will be calculated as: Change from baseline = post baseline value – baseline value.

Confidentiality Statement

Philip Morris Products SA.	Statistical Analysis Plan	Confidential
P1-EXC-01-EU	Final 2.0	Page 35 of 71
Related to PMI-RRP-WKI-112487		

For log-transformed variables, the (relative) change from baseline is defined as: Change from baseline = log(post baseline value / baseline value).

For step count, the baseline will be the average steps taken between V2 and V3.

Time variables, i.e. exercise capacity and time spent at different percentages of maximal work rate (or maximal HR) during each training session will be analyzed in seconds (not in min:sec).

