9.1.3.1 Analysis Period

In general, the analysis will be performed at a visit(s) level but in the case where data is collected more frequently for example the Mhealth or exercise training data we define the analysis period by month. Here, Week 1 is the period between V3 and V4, Month 1 is described as the period between V5 up to the date of V14, Month 2 is the day after V14 and until the date of V28 and Month 3 represents the day after V28 until the date of V43.

For certain endpoints (see section 9.6.1.2) related to $VO2_{max}$ and exercise capacity the analysis period Week 1 and Month 3 will have different baseline values dependent on the subject's product use group during the corresponding period for the calculation of the descriptive statistics.

9.1.4 Handling of Dropouts, Missing Data (Including Outside the Limits of Detection or Quantification) or Partial Data

Dropouts (discontinued subjects) and other subjects with missing data will be analyzed in the analysis set(s) when data are available, without imputation of missing data.

No imputation schemes for missing values will be applied.

For laboratory parameters outside the limit of detection or quantification, the following imputation will be performed:

- Values below the lower limit of detection (LLOD) or quantification (LLOQ) will be imputed as 0.5 x LLOD or LLOQ.
- Values above the upper limit of detection (ULOD) or quantification (ULOQ) will be imputed as the ULOD or ULOQ.

The number of values below LLOD (or LLOQ) or above ULOD (or ULOQ) will be presented in each summary table, as well as the statistics on the other quantitative values.

However, if 50% or more data are below the lower limit or above the upper limit, only the number of values below the lower limit and above the upper limit will be reported in the

Confidentiality Statement

Philip Morris Products SA.	Statistical Analysis Plan	Confidential
P1-EXC-01-EU	Final 2.0	Page 36 of 71
Related to PMI-RRP-WKI-112487		

summaries, together with minimum (if no value below the lower limit is present) and maximum (if no value above the upper limit is present) of the observed values, and no other statistics will be reported.

There will be no imputation of missing laboratory parameters.

For product use data that are missing:

• There will be no imputation and all available data (ePRO and/or paper) will be analyzed as is.

For bike training data that is incomplete:

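### The step-count section's example code omits the baseline covariate that its text lists, and its text starts Month 1 at V4 although SAP 9.1.3.1 starts it at V5

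*SAP*

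**What the plan says.** **Outcome and covariates.** In SAP 9.6.1.1.5, "the dependent variable will be the average step count by month". It is a level, not a change from baseline. The covariate sentence names arm, visit, their interaction, sex, age and V1 cigarette consumption, and ends: "baseline step count (see section 9.1.3) will be considered as covariates, subject will be used as a random effect". SAP 9.1.3 defines the baseline: "For step count, the baseline will be the average steps taken between V2 and V3".

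**Code.** The section continues: "An example of SAS code for the model to be used is provided below". The MODEL statement is "model ENDPOINT = ARM SEX AGE CC_CONS_GRP MONTH MONTH*ARM /ddfm = kr". Every listed covariate appears (visit coded as MONTH) except the baseline step count.

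**Periods.** The monthly outcome is obtained by "averaging the daily step count from V4 to V14 (Month 1), V14 to V28 (Month 2) and V28 to V43 (Month 3"). SAP 9.1.3.1 sets the months for densely collected data, gives mHealth as an example, and states: "Month 1 is described as the period between V5 up to the date of V14". There Week 1 is V3 to V4, Month 2 begins the day after V14 and Month 3 the day after V28. Nothing says that 9.6.1.1.5 overrides 9.1.3.1, or whether text or code prevails where they differ.

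**The concern.** Because the outcome is the monthly level, the baseline covariate is the model's only adjustment for how active a subject was before randomisation. The random subject effect does not do this job. It models correlation among a subject's own months and leaves a baseline difference between groups inside the arm contrast. Randomisation does not remove that difference either. The endpoint is analysed in the AEECS by actual product use, and outside IQOS-2 the set requires at least 34 of 38 training sessions, so the groups are formed partly by behaviour after randomisation.

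The month boundaries matter because V5 is the first training visit. A Month 1 that opens at V4 averages days before training with days during it. Daily physical activity is one of the five main goals in Protocol 2.2, and the protocol synopsis singles out the IQOS-1 versus IQOS-2 comparison of activity levels. As written, two programmers could each follow the SAP and produce different models on different days.

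**Working it through.** The plan states no figure to reproduce here. The check sets the text against the code and then does the visit-day arithmetic.

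**1. Covariates, text against code**

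| Listed in the text | In the MODEL statement |
|---|---|
| Arm | ARM |
| Visit, Visit by Arm | MONTH, MONTH*ARM |
| Sex, age | SEX, AGE |
| V1 cigarette consumption | CC_CONS_GRP |
| Baseline step count | absent |

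The example code in the next section (9.6.1.1.6, biological health markers) does include a BASELINE term.

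**2. Precision lost without the baseline**

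In the simple single-outcome ANCOVA approximation, SE without baseline / SE with baseline = 1/sqrt(1 − r²). Here r is the correlation between baseline and monthly steps within arms, after the other covariates. The documents give no value, so I assume 0.3 to 0.8.

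| r | 1 − r² | SE ratio |
|---|---|---|
| 0.3 | 0.91 | 1.05 |
| 0.5 | 0.75 | 1.15 |
| 0.6 | 0.64 | 1.25 |
| 0.7 | 0.51 | 1.40 |
| 0.8 | 0.36 | 1.67 |

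The unadjusted contrast also shifts by (slope of monthly on baseline steps) × (baseline difference between the groups). That difference is unknown before the data are seen, so I put no number on it.

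**3. Days before training in the V4-based Month 1**

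Planned days after V3: V4 = 7±2 and V5 = 15±2 (Protocol 4.1); V14 = 40±2 and V28 = 68±2 (Protocol 9.4.2); V43 = 106±2 (Protocol 9.4.3). Days are counted inclusively.

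- V4 to V14: 40 − 7 + 1 = 34 days.
- V5 to V14: 40 − 15 + 1 = 26 days.
- Before training: 34 − 26 = 8 days, and 8/34 = 23.5%.
- Across the V3-based windows: the lowest share is 4/34 = 11.8% (V4 day 9, V5 day 13, V14 day 42) and the highest 12/34 = 35.3% (V4 day 5, V5 day 17, V14 day 38).
- Protocol 9.4.2 also puts training 7±1 days after V4. Holding the gap to 6 to 8 days within the same windows gives 6/36 = 16.7% to 8/30 = 26.7%.

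Suppose a step difference is zero before V5 and constant from V5, with valid days spread evenly. It is then reported at 26/34 = 76% of its size (65% to 88% across the V3-based windows).

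**4. Shared dates**

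Under 9.6.1.1.5, Month 2 is days 40 to 68 (29 days) and Month 3 is days 68 to 106 (39 days). Under 9.1.3.1 they are 28 and 38 days. The overlap is one date at each boundary.

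**The case against.** **The prose already specifies the right model.** The code is labelled an example, and the covariate sentence is the section's only list. Example code elsewhere in the SAP is not always literal: the lactate example in 9.6.1.1.4 has oxygen uptake as its response. This stands to the extent that the loss arises only if the code is followed. A reader might infer that the planned analysis has no baseline adjustment at all; the documents do not support that. Nor is the baseline optional because it is only to be considered as a covariate, since the same phrase governs arm, sex and age.

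**The V4 start is in the text, not the code.** True. The code contains no visit boundaries, so correcting the MODEL statement alone would leave the period conflict in place.

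**The V4 to V5 days are legitimate data for some contrasts.** Product use changes at V3. For IQOS-1 or SA against cigarette these days follow the switch and precede training in both groups, so a V4 start is defensible. This stands and confines the dilution mainly to IQOS-1 versus IQOS-2. Under 9.1.3.1 those days belong to no period, a cost that any correction should state.

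**The descriptive table may still match the model.** A reader might infer that the modelled and descriptive months must differ. SAP 9.6.1.2.5 says only that steps are reported by month and does not cite 9.1.3.1. A mismatch is likely, because 9.1.3.1 names mHealth data, but it is not certain.

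**The size is uncertain and the stakes modest.** The correlation is assumed, the baseline rests on about a week of wear, and sex, age and cigarette stratum already explain part of the variation. The study is descriptive with no hypothesis test. Baseline is plotted beside Months 1 to 3, and changes from baseline are summarised, so an imbalance would be visible. These points limit the priority but resolve neither contradiction.

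**Conclusion.** Both contradictions are in the SAP, and they are more than clerical because they lead to different models and different analysis days.

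If the code is followed, the between-arm standard error is larger by roughly 5% to 67%, given an assumed correlation of 0.3 to 0.8 and a simple ANCOVA approximation applied to a repeated-measures model. The contrast also keeps whatever baseline difference exists between the actual-use groups. If the text's months are followed, about 24% of Month 1 (12% to 35% across visit windows) precedes training. That dilutes mainly the Month 1 IQOS-1 versus IQOS-2 contrast, and only if the difference begins with training. The shared V14 and V28 dates are an inconsistency of negligible size.

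The documents do not show that the step-count results will be biased or that the baseline has been left out by design. They leave the choice open. It should be settled, but it does not threaten the study's main results.

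**What to change.** - In SAP 9.6.1.1.5, add the V2 to V3 baseline step count to the MODEL statement so that the code matches the text.
- Replace the months in that section with those of 9.1.3.1: Month 1 from V5 to V14, Month 2 from the day after V14 to V28, Month 3 from the day after V28 to V43.
- State that the days after V4 and before V5 are excluded from Month 1, or report them as a period of their own (after the switch, before training).
- State how subjects without valid V2 to V3 days are handled.

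The cost is one code term and a few sentences, with no new data. About 8 post-switch days per subject leave the Month 1 average, and subjects without a valid baseline drop out of the model unless a fallback is stated.
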